14.4.1 Secondary Endpoint: Sensitivity Analysis for PFS

PFS as assessed by the Investigator will be described in the same way as the PFS as assessed by IRC using rules for censoring defined in [Table 8](#) and [Table 9](#).

These sensitive analyses will be supported with Kaplan-Meier plot and a listing as described in section 14.4.

CCI

14.6 Secondary Endpoint: Duration of Response

Duration of Response (DOR) is defined for participants with a confirmed objective response as the time from first documentation of a confirmed objective response (CR or PR) according to RECIST 1.1 to the date of first documentation of objective progression of disease (PD) or death due to any cause, whichever occurs first. The censoring rules for DOR are as described for PFS (Table 8 and Table 9).

$$DOR \text{ (months)} = \frac{(date \text{ of } PD \text{ or death or censoring} - date \text{ of confirmed objective response} + 1)}{30.4375}$$

DOR of confirmed CR/PR according to RECIST 1.1 as measured by the IRC and the Investigator will be described. The date of occurrence of the first CR/PR will be used as date of objective response.

Frequency (number and percentage) of participants with an event will be presented as well as the DOR time Med, Min, and Max. Number of participants at risk, failed and DOR rates with their CI at 3, 6, 9, 12, 18 and 24 months will also be provided.

The analysis of DOR will be performed with a Kaplan-Meier method (product-limit estimates) and a summary of associated statistics will be presented including corresponding two-sided 95% CIs. The CIs for the Med will be calculated according to Brookmeyer and Crowley (1982) and CIs for the survival function estimates will be derived using the log-log transformation according to Kalbfleisch and Prentice (1980) (CONFTYPE = loglog default option in SAS PROC LIFETEST). The estimate of standard error will be computed using Greenwood's formula.

The time to and duration of response per participant having a confirmed objective response will be displayed in swimmer graphs. Kaplan-Meier figures will also be provided.

A listing for responders will be provided with the following information: participant identifier, age, sex, race, date of first study treatment administration, date of first response, date of last tumor assessment, censored (Y/N), date of event/censoring, event/censoring reason, duration of response and if the response is ongoing (administrative censoring for subject ongoing in the study without an event). This listing will be sorted by participant identifier.

Exploratory subgroup analyses for DOR, using the subgroups defined in section 8.2 will be performed using Kaplan-Meier figures. Participants with missing subgroup category will not be included in the related subgroup analysis.

Durable Response Rate (DRR) is defined as the number of participants having a DOR of at least 6 months, out of the total number of participants. Participants for whom the DOR is censored will be treated as not having a DOR of at least 6 months.

The number of participants with DRR will be tabulated and a two-sided 95% CI for percentage using the Clopper-Pearson method (exact CI for a binomial proportion as computed by default by the FREQ procedure using the EXACT option).

DRR will be described according to RECIST 1.1 as measured by the IRC and the Investigator.

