9.4 Statistical Analyses

Full details of all planned analyses will be described in the study Integrated Analysis Plan (IAP). Major modifications of planned analyses will be reflected in a protocol amendment or in the clinical study report (CSR).

In general, continuous variables will be summarized using number (n), mean, median, standard deviation, minimum, and maximum. Categorical variables will be summarized using frequency counts and percentages. Proportions are calculated based on the number of participants in the analysis set of interest, unless otherwise specified in the IAP.

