9.4.1 Efficacy Analyses

Analysis of efficacy variables will also be performed on the Full Analysis Set (FAS) as well as subgroup of interest as listed in [Table 3](#), including but not restricted to PD-L1 expression.

Statistical analysis methods for primary and key secondary efficacy endpoints are summarized in Table 11. Further details will be specified in the IAP.

Table 11 Statistical Analysis Methods for Efficacy Analysis

Endpoint	Statistical Analysis Methods
Primary	
Confirmed objective response according to RECIST 1.1 assessed by an IRC	The ORR will be determined as the proportion of participants with a confirmed objective response of PR or CR. Confirmation of the response according to RECIST 1.1 will be required no sooner than 4 weeks after the initial documentation of CR or PR. The 95% CI for the ORR will be calculated using the Clopper-Pearson method.
Key Secondary	
DOR assessed by an IRC	DOR is defined as the time from first documentation of a confirmed objective response (CR or PR) according to RECIST1.1 to the date of first documentation of objective response of disease progression (PD) or death due to any cause whichever occurs first. The censoring rules for DOR are as described below for PFS. Kaplan-Meier estimates will be provided;

Endpoint	Statistical Analysis Methods
	Median DOR and the 95% CI for the median will be calculated according to Brookmeyer and Crowley (Brookmeyer 1982); Swimmer plots will be provided.
Durable response assessed by an IRC	A durable response is defined as an objective response (CR or PR) according to RECIST 1.1, determined by an IRC, with a duration of at least 6 months. Participants for whom the DOR is censored will be treated as failures (successes) in the analysis of durable response if the censored DOR is before (at least) 6 months. The DRR is defined as the percentage of participants with durable response. The 95% CI for the DRR will be calculated using the Clopper-Pearson method.

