4.1 Early Discontinuation of the Study

Due to the decision to early discontinue the study, not all the analyses described in this IAP will be provided. Especially, no analyses for efficacy, pharmacokinetics, immunogenicity, or biomarkers will be performed. Due to the low number of participant listings will be delivered for all other endpoints instead of summary tables as deemed appropriate and will be included in an abbreviated CSR.

5 Objectives and Endpoints

Table 1 Study Objectives and Endpoints

Objectives	Endpoints (Outcome Measures)	IAP section
Primary		
To evaluate clinical efficacy of bintrafusp alfa in participants with TNBC with high HMGA2 expression, based on ORR	Confirmed objective response according to RECIST 1.1 assessed by an IRC	14.1
Secondary		
To evaluate clinical efficacy of bintrafusp alfa based on DOR	DOR according to RECIST 1.1 assessed by an IRC	14.6
To evaluate clinical efficacy of bintrafusp alfa based on DRR	Durable response of at least 6 months assessed by an IRC	14.6
To evaluate clinical efficacy based on PFS	PFS according to RECIST 1.1 assessed by an IRC	14.4
To evaluate ORR, DOR, DRR, and PFS by Investigator read	Objective response, DOR, Durable response, and PFS according to RECIST 1.1 as assessed by the Investigator	14.2 14.6 14.4
To evaluate clinical efficacy based on OS	OS	14.7
To evaluate clinical safety of bintrafusp alfa	Occurrence of TEAEs and treatment-related AEs including AEs of special interest	15.1 15.2
To characterize the PK profile of Bintrafusp alfa	
 The concentration observed immediately at the end of infusion (C_{EOI}) of bintrafusp alfa The concentration observed immediately before next dosing (corresponding to predose or trough concentration [C_{trough}] for multiple dosing) of bintrafusp alfa 	16.1 16.2
To characterize the immunogenicity of bintrafusp alfa	Immunogenicity of bintrafusp alfa as measured by ADA assay from Screening through Safety Follow-up Visit up to 28 days after last treatment	16.3
CCI		

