6.2 Primary Analysis

This analysis will be the main analysis and all planned analyses identified in the Clinical Study Protocol and in this IAP will be performed. All data will be included up to a clinical cut-off date corresponding to 8 months after the accrual of the last participant.

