7.1 COVID-19 Impact

No changes to the planned analysis of the efficacy endpoints will be performed due to the impact of COVID-19 outbreak.

Instead, given the low number of subjects included in the study, additional tags and labels will be used to identify Protocol Deviations (PDs) and AEs related with COVID in listings. See sections 10.2 and 15.1.1 for more details.

8 Analysis Populations and Subgroups

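### SAP 14.6 scores every censored response as not durable, against protocol Table 11, so a response still ongoing at 7.4 months becomes a DRR failure

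*SAP*

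**What the plan says.** Protocol section 9.4.1, Table 11 (durable response assessed by the IRC), splits censored durations at 6 months. Participants with a censored duration of response (DOR) "will be treated as failures (successes) in the analysis of durable response if the censored DOR is before (at least) 6 months".

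SAP section 14.6 first defines the DRR as the share of all participants whose DOR is at least 6 months. It then adds, with no time qualifier: "Participants for whom the DOR is censored will be treated as not having a DOR of at least 6 months".

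Two further SAP provisions determine who is censored. Section 14.6 applies the PFS censoring rules to the DOR, and section 14.4 censors a participant without progression or death at the last adequate tumor assessment. Section 14.6 itself describes an ongoing response as administratively censored in the responder listing.

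The DRR belongs to the primary analysis. Protocol section 9.4.4 schedules it then in support of the ORR, and SAP section 6.2 sets the cut-off: "All data will be included up to a clinical cut-off date corresponding to 8 months after the accrual of the last participant".

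**The concern.** The two rules agree for a response censored before 6 months: both fail it. They disagree for a response censored at 6 months or later, where 6 months of response has already been observed. The protocol accepts that observation and the SAP discards it.

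The result is a perverse ordering. A participant who progresses at 7 months counts as a durable responder, while one still responding at 7 months does not. At a cut-off 8 months after last accrual, the longest responses are the ones most likely to be ongoing, so the rule penalises the outcome the endpoint is meant to capture. The two documents would give different DRRs and confidence intervals from the same data.

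The departure is not declared. SAP section 7, where changes from the protocol belong, holds only the COVID-19 item: "No changes to the planned analysis of the efficacy endpoints will be performed due to the impact of COVID-19 outbreak". Protocol section 9.4 also allows another place of record ("Major modifications of planned analyses will be reflected in a protocol amendment or in the clinical study report (CSR"), but the current protocol still carries the opposite rule. No other part of the SAP restores it.

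**Working it through.** **Design figure.** The protocol synopsis gives an 81% probability that the exact 95% lower limit exceeds 10% when the true ORR is 30% and N = 29. The smallest qualifying count is 7/29 (lower limit 10.3%; 6/29 gives 8.0%), and the exact binomial probability of 7 or more is 81.2%. The figure reproduces; the point here does not depend on it.

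**Worked participant, from document inputs only.**
- Scans (SAP 14.4): days 57, 113, then every 8 weeks, so 169, 225, 281, 337.
- DOR (SAP 14.6) = (date of PD, death or censoring − date of first CR/PR + 1) / 30.4375.
- Six months = 6 × 30.4375 = 182.6 days.
- Response first seen on day 57, ongoing at the day 281 scan: (281 − 57 + 1) / 30.4375 = 225 / 30.4375 = 7.39 months, censored. Protocol: durable. SAP: not durable.
- Same participant with PD on day 281: 7.39 months, event. Durable under both.
- Previous scan: (225 − 57 + 1) / 30.4375 = 169 / 30.4375 = 5.55 months. If censored there, a failure under both.

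The 8-month cut-off is 8 × 30.4375 = 243.5 days after last accrual. The day 281 scan therefore falls before cut-off only for participants who entered at least 281 − 243.5 = 37.5 days (about 38) before the last one.

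**Effect on the estimate, assumed counts.** Suppose 5 of 29 participants have responses of at least 6 months, giving a protocol DRR of 5/29 = 17.2% (Clopper-Pearson 95% CI 5.8 to 35.8). The SAP DRR depends on how many are still ongoing:

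| Ongoing among the 5 | SAP DRR | 95% CI |
|---|---|---|
| 2 | 3/29 = 10.3% | 2.2 to 27.4 |
| 4 | 1/29 = 3.4% | 0.1 to 17.8 |
| 5 | 0/29 = 0% | 0 to 11.9 |

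**Expected DRR under a model.** The documents give no expected DOR or accrual time, so the following are assumptions:
- ORR 30%; first response at scan 1, 2 or 3 in 65%, 25% and 10%.
- No PD at the scan after first response, because the SAP states that "Duration of Response (DOR) is defined for participants with a confirmed objective response". The true duration is then 56 days plus an exponential with mean (median − 56 days) / ln 2.
- Uniform accrual, no loss to follow-up, nominal scan days (every 84 days after day 337), PD dated at the next scan, cut-off 8 months after last accrual.

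With 12-month accrual:

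| Median DOR (months) | Protocol rule | SAP rule | Gap (points) |
|---|---|---|---|
| 3 | 2.7% | 2.5% | 0.3 |
| 4 | 7.6% | 5.8% | 1.8 |
| 6 | 13.3% | 7.6% | 5.8 |
| 9 | 17.2% | 6.9% | 10.3 |
| 12 | 19.2% | 5.9% | 13.3 |
| 18 | 21.0% | 4.4% | 16.6 |

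(Gaps are from unrounded values.) At a 12-month median this is about 0.192 × 29 = 5.6 against 0.059 × 29 = 1.7 participants. Above a median of about 6 months, the SAP's DRR falls as responses lengthen. Over medians of 3 to 18 months and accrual of 6 to 18 months, the protocol rule gives 2.1 to 22.6%, the SAP rule 1.7 to 9.8%, and the gap is 0.2 to 16.6 points.

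**Sensitivity at 12-month accrual, medians 3, 6 and 12 months (protocol vs SAP).**
- PD at its true date: 2.2 vs 2.1%, 12.6 vs 7.9%, 18.7 vs 6.5%.
- First response at scans 1/2/3 in 40/30/30%: 2.5 vs 2.2%, 12.0 vs 6.6%, 17.2 vs 5.1%.
- Hazard fixed at ln 2 / median, conditioned on no PD at the next scan: 10.5 vs 7.0%, 16.1 vs 7.3%, 19.9 vs 5.4%. Here the median among confirmed responders is 56 days longer than nominal.

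**The case against.** The strongest objection is practical. SAP section 4.1 records that the study is being stopped early: "Especially, no analyses for efficacy, pharmacokinetics, immunogenicity, or biomarkers will be performed". Under that plan no DRR will be reported. DRR is also secondary and descriptive, with no test attached, and the primary ORR is untouched. All of this stands. It limits the present consequence, but section 14.6 remains in the current SAP and contradicts the protocol.

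Other output would soften the effect. Section 14.6 also plans Kaplan-Meier DOR rates at 6 months and other times, swimmer plots, and a responder listing that flags ongoing responses. The 6-month Kaplan-Meier rate handles censoring properly, but it is conditional on response and does not replace a rate over all participants.

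The size rests on assumptions and shrinks with follow-up. In the same model with 12-month accrual, moving the cut-off to 24 months after last accrual reduces the gap from 5.8 to about 0.7 points at a 6-month median, and from 13.3 to about 6.0 at 12 months. SAP section 6.3 does not say whether the DRR is repeated then.

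The sentence may simply have lost a qualifier in drafting; the literal text still needs correcting. The SAP's modification history is silent on the DRR, but it compares SAP versions, so little follows from that.

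Finally, the stricter rule could be kept and declared in SAP section 7. That would remove the inconsistency but still score observed 6-month responses as failures. Conservatism is no defence, because the protocol already fails responses censored before 6 months.

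**Conclusion.** The concern holds. The two rules cannot both be applied, and the SAP's is wrong as written: it biases the DRR downward whenever a response of 6 months or more is censored. The contradiction and the 7.39-month example follow from the documents alone. The size does not. It is negligible for short responses and reaches 16.6 points in the scenarios examined, all of which rest on assumed DOR, accrual and response timing. It should be fixed, although a reported result changes only if the DRR is actually analysed.

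**What to change.** Replace the sentence on censored DOR in SAP section 14.6 with the protocol's rule: a DOR censored before 6 months counts as not durable, and a DOR censored at 6 months or later counts as durable. Apply it to both the IRC and Investigator versions of the DRR.

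The cost is one sentence, with no new data, assessments or analyses. If SAP section 4.1 is followed and no DRR is produced, the correction is for the record only.

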14.7 Secondary Endpoint: Overall Survival

Overall survival (OS) is defined as the time from first administration of study treatment to the date of death due to any cause:

$$OS \text{ (months)} = \frac{(date \text{ of event or censoring} - date \text{ of first dose} + 1)}{30.4375}$$

For participants alive at the time of data cut-off date or who are lost to follow up, OS will be censored at the last date known to be alive. The date of event/censoring is defined in Table 10.

Table 10 Date of event/censoring definition for OS analysis

Survival Status		Source	Censoring	Date of event/censoring
Died	Before cut-off	Death eCRF	Event	Date of death
	After cutoff	Death eCRF	Censored	Date of cutoff
Alive (no date of death)	Alive after cut-off	FU eCRF	Censored	Date of cut-off
	Otherwise	Date of last known to be alive, see Section 9.6		Censored
eCRF: electronic case report form, FU: follow-up.				

The analysis of OS time will be performed with a Kaplan-Meier method with the same approach as for PFS described in section 14.4. Kaplan-Meier estimates (product-limit estimates) will be presented together with a summary of associated statistics including corresponding two-sided 95% CIs. OS rates with their CI at 3, 6, 9,12, 18 and 24 months will be presented, as well as the number of participants at risk and failed. Censoring reasons will also be described. Censoring reasons are as follows:

- Alive at cut-off date
- Withdrawal of consent
- Lost to follow-up

OS will also be presented graphically with Kaplan-Meier figures.

A participant listing will provide the following information: participant identifier, age, sex, race, date of first study intervention, date of event/censoring, event/censoring reason, time to event. This listing will be sorted by participant identifier.

CCI

CCI

15 Safety Analyses

Analysis set: SAF

The subsections in this section include specifications for summarizing safety endpoints that are common across clinical studies such as adverse events, laboratory tests and vital signs.

15.1 Adverse Events

Treatment-emergent adverse events (TEAEs) are those events with onset dates occurring during the on-treatment period or if the worsening of an event is during the on-treatment period (see on-treatment definition in section 9.8).

Changes in toxicity grade, seriousness or outcome of AEs are recorded as separate entries in the eCRF. Such entries reporting the same event in such immediately consecutive periods will be considered as one event in the analysis (using the field “AE id for new grade” in the eCRF). These events will be kept as separate records in the database in order to maintain the full detailed history of the events. The start date of the initial record in the sequence is taken as start date of the entire event, similarly the end date of the last event in the sequence is taken as end date of the entire event. The overall outcome of the adverse event is the outcome of the last event in the sequence. Duration of the AE and the TEAE flag will be adjusted accordingly in the analysis.

Incomplete AE-related dates will be handled as stated in section 9.9.

Related Adverse Events are those events with relationship to study treatment (as recorded on the “Adverse Events Details” eCRF page, Relationship with Bintrafusp alfa= Related) reported by the Investigator and those of missing or unknown relationship.

Serious Adverse Events (SAE) are those events reported on the “Adverse Events Details” eCRF page, with the “Serious Adverse Event” field ticked “Yes”.

Adverse Events Leading to Temporary Discontinuation are those events leading to temporary discontinuation of study treatment (answer to the question “Action(s) taken with Bintrafusp alfa” = “Drug interrupted” on “Adverse Event Details” eCRF page).

Adverse Events leading to Permanent Treatment Discontinuation are those events leading to permanent discontinuation of study treatment (answer to the question “Action(s) taken with Bintrafusp alfa” = “Drug withdrawn” on “Adverse Event Details” eCRF page).

Adverse Events leading to Death are those events leading to death (as recorded on the “Adverse Event Details” eCRF page, change in grade = “No” and outcome = “Fatal”, or Grade = “Grade 5 or death related to AE” or Serious adverse event = “Yes” and seriousness criteria include “Results in death”).

Adverse Events of Special Interest (AESI): AESI are identified according to a pre-specified search list of MedDRA Preferred Terms (PTs) which will be finalized before the database lock. Categories of AESI include:

- Infusion-Related Reactions (IRRs)
- Immune-Related Adverse Events (irAEs)
- Skin AEs possibly related to TGF- β inhibition
- Anemia

Bleeding events are those events belonging to the MedDRA SMQ Haemorrhage terms (excluding laboratory terms).

All analyses described in this section will be based on TEAEs if not otherwise specified. The AE listings will include all AEs. AEs outside the on-treatment period (prior or after) will be flagged in listings. AE occurring during the reinitiation phase will be considered as TEAE and will be reported in the summary tables and will be flagged in the listings.

15.1.1 All Adverse Events

Adverse events will be summarized by worst severity (according to National Cancer Institute - Common Terminology Criteria for Adverse Events [NCI-CTCAE] version 5.0) per participant, using the latest available version of MedDRA PT at the time of the database lock as event category and MedDRA primary SOC body term as Body System category.

Unless otherwise stated adverse events will be displayed in terms of frequency tables: primary SOCs and PTs in alphabetical order.

If an adverse event is reported for a given participant more than once during treatment, the worst severity and the worst relationship to study treatment will be tabulated. In case a participant had events with missing and non-missing grades, the maximum of the non-missing grades will be displayed.

A table presenting the overall summary of AEs will be presented including the frequency (number and percentage) of participants within each of the following categories:

- TEAEs
- Related TEAEs
- Serious TEAEs
- Related Serious TEAEs
- TEAEs NCI-CTCAE severity grade (≥ 3 , ≥ 4)
- Related TEAEs NCI-CTCAE severity grade (≥ 3 , ≥ 4)
- TEAEs leading to death
- Related TEAEs leading to death
- AEs of special interest:
 - Infusion-related reactions (IRRs)
 - Immune-related AEs (irAEs)
 - Potential TGF β inhibition mediated skin Aes
 - Bleeding events
 - Anemia
- Related AEs of special interest:
 - Infusion-related reactions (IRRs)
 - Immune-related Aes (irAEs)
 - Potential TGF- β -mediated skin Aes
 - Bleeding events
 - Anemia

Tables for TEAEs frequency corresponding to each category in the overview table above will be provided by:

- MedDRA primary SOC (ordered alphabetically) and PT (ordered alphabetically), (except for AE of special interest and TEAE with NCI-CTCAE severity grade ≥ 3 or ≥ 4).

TEAEs and related TEAEs by worst grade will also be summarized, and the most frequent PTs (at least 5%) will be presented graphically by worst grade and PT with bar chart figures.

Clinicaltrials.gov and EudraCT - requirements

Summary table for non-serious TEAEs excluding SAEs applying frequency threshold of 5% will be provided.

Listings of adverse events will contain the following information: participant identifier, age, sex, race, first and last date of study intervention, PT, reported term for the AE, start date, end date, duration of AE (in days), day relative to the first infusion, day relative to the most recent infusion prior to AE onset, relationship to study treatment, toxicity grade, action(s) taken, outcome,

seriousness (Y/N), AESI infusion-related (Y/N), AESI immune-related (Y/N), potential TGF- β -mediated skin AESI (Y/N), bleeding event AESI (Y/N), anemia AESI (Y/N) and AE occurring after COVID-19 pandemic start (Y/N). TEAEs and AEs occurring during the reinitiation period specifically will be flagged. This listing will be sorted by participant identifier, start and end date and PT.

The following listings will be provided with the relevant information:

- Listing of all AEs (whether treatment-emergent or not) (TEAEs will be flagged; AEs occurring during reinitiation phase will be flagged)
- Listing of TEAEs
- Listing of non-TEAEs for AEs starting and not worsening after enrollment (date of first signature of informed consent/date of first signature of first informed consent) but prior to the first dose of study intervention.
- Listing of AEs with onset or worsening after the on-treatment period (AEs occurring during reinitiation phase will be flagged)
- Listing of all AEs for reinitiated participants (AEs occurring during reinitiation phase will be flagged)

Evaluation of Potential Effect of ADA on Bintralusp alfa Safety

The overall summary of TEAEs table, as described above will also be provided by ADA status (ever positive, never positive). See section [16.3](#) and [Table 15](#) for ADA status details.

Listings of all AEs and all IRRs for ever-positive ADA participants (pre-existing, transient treatment-emergent, persistent-treatment emergent) will be prepared including participant identifier and showing the date(s) of the positive ADA result together with the AEs or IRRs. For the AEs and IRRs, start and stop date will be shown along with grade. Adverse events recorded during the period of 2-weeks prior to the positive ADA value till two weeks after the positive ADA value will be flagged.

